
6. Identify challenges associated with implementation of routine plasma CrAg screening in clinics providing HIV care
	
 
• Percentage of patients with <math>CD4 < 100</math> cells/<math>\mu</math>L who are lost to follow-up or have incomplete documentation
 
• % of patients with no documented clinic visit 30, 60, and 90 days after date of the scheduled clinic appointment
 

7. To disseminate lessons learned with participating sites
	
 
• Reflection and transition workshop
 

8. To estimate the costs of implementing CrAg screening based on data to be collected at 22 participating OPCs participating in Phase 1 and provider costs associated with CM treatment.
	
 
• Total costs and unit cost per person screened, per CrAg+ treated by site, lab facility type, and cost component
 

9. To conduct an incremental cost-effectiveness analysis of CrAg screening compared with a standard of care (no CrAg screening, and treatment for symptomatic CM only).
	
 
• Incremental cost-effectiveness ratio (cost per CM death averted and cost per quality adjusted life year (QALY))
 

10. To project potential cost savings from implementing CrAg screening and financial resources required to implement CrAg screening under different scale-up scenarios and for national rollout.
	
 
• Total cost savings and amount of financial resources required to implement CrAg screening
 

11. To determine the prevalence of Talaromyces marneffei antigenemia (TmAg) in stored CRICS samples using the Mannose phosphate isomerase 1 (MP1) enzyme-linked immunosorbent assay (ELISA)
	
 
• Proportion of stored samples that test positive for TmAg
 

12. To assess the impact of TmAg positivity on mortality
	
 
• Six (6) and twelve (12) month all-causes and TM-related mortality among patients who screen TmAg-positive and TmAg-negative
 

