###### **Medical and past history**

- HIV-related (Date HIV testing/diagnosis, CD4 count, HIV Staging, OIs)
- Past history (diabetes, hypertension, kidney failure, heart failure, stroke, chronic obstructive pulmonary disease)

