### **10.3. TmAg in Stored Samples (Sub-study)**

*Talaromyces* (formerly *Penicillium*) *marneffei* is a dimorphic fungus that causes a life-threatening infection in immunocompromised individuals living and traveling in Southeast Asia, China, and India[24, 25]. Talaromycosis is a leading cause of AIDS-related deaths, trailing only TB and cryptococcosis, accounting for 4-15% of AIDS admissions in endemic regions[26-28]. Patients present very late in the course of illness, which has significant treatment morbidity and a mortality rate of up to 30%; treatment options remain limited[26-28]. The recent development of point-of-care cryptococcal LFA (such as CrAg®LFA) has allowed early diagnosis and prevention of CM by pre-emptive fluconazole therapy. The approach is shown to reduce HIV mortality[29], is cost effective in low- and middle-income countries[7, 10]and is in the treatment guidelines in 20 countries.

Stored samples from the CRICS study provides the perfect opportunity to retrospectively investigate the prevalence and clinical significance of TmAg, as the patient population at risk for cryptococcosis is also at risk for talaromycosis.

We will use a novel TmAg detection ELISA developed by the University of Hong Kong for screening[30]. The assay has been validated in the Oxford University Clinical Research Unit (OUCRU) laboratory in Vietnam in more than 600 HIV-infected patients with and without culture-confirmed talaromycosis. The ELISA has the sensitivity and specificity of above 90% and is more sensitive than blood culture in diagnosing talaromycosis (unpublished data). This assay was able to detect TmAg in 9.4% of more than 8,000 archived serum specimens from patients attending HIV clinics in Guangzhou, China[31]. Linked clinical data were not available in that study; therefore the clinical significance of TmAg could not be assessed. Mortality and other clinical outcome data from Phase 1 of the CRICS study will be used to assess clinical significance of antigenemia.

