## Cryptococcal Retention In Care Study (CRICS)

We hypothesize that the prevalence of TmAg in HIV-infected individuals with CD4 counts  $\leq 100$  cells/ $\mu$ L will be at least 5%, and that asymptomatic TmAg is associated with a higher all cause morbidity and mortality.

This study will provide further evidence for the MOH on the potential role of screening for TmAg (and pre-emptive itraconazole therapy for TmAg-positive patients), an approach that may substantially reduce the excess morbidity and mortality in patients starting ART in Tm endemic regions in Asia.

Nearly all patients enrolled in CRICS agreed to the storage of blood specimens for later use; stored samples are identified only by study ID number. All available specimens will be tested for TmAg by ELISA in the OUCRU laboratory in Vietnam. The assay requires 500 mcl plasma out of 500-1000 mcl stored samples.

The study team will match the specimen's ID with the patient's ID as much as possible to ensure that positive TmAg results are returned to the primary doctors who are responsible for the clinical care for the patients. Secondly, doctors in OPCs with positive TmAg patients will be notified about the number of positive tests among their enrolled patients so as to increase their index of suspicion for *T. marneffei* infection. We hope that this will encourage providers to conduct intensive screening for symptoms of Talaromycosis during subsequent patient visits.

Because TmAg is not the nationally approved laboratory test for diagnosis of *T. marneffei* infection in Vietnam, there is no official recommendation for treating asymptomatic patients who are TmAg positive. The decision on antifungal treatment will be made by the primary physicians based on local practice. The treatment regimen for those who are symptomatic will be determined by the primary physician on a case-by-case basis and will follow the standard of care at OPCs in accordance with national guidelines. Per the national guideline the treatment includes amphotericin B (0.7 -1,5 mg/kg/day) for 2 weeks, then itraconazole 200 mg bid (in children 5-6 mg/kg bid) x 8- 10 weeks) or for mild cases or when Amphotericin B is unavailable, itraconazole 200 mg bid x 8 weeks. Maintenance therapy includes itraconazole 200 mg/day in adults and

Funding will be contributed by OUCRU to test specimens for TmAg.

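### Objective 12 compares mortality in all TmAg-positive and all TmAg-negative patients, which does not test the section 10.3 hypothesis about asymptomatic antigenemia and can be inflated by overt talaromycosis at enrollment

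*Protocol*

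**What the plan says.** Table 1 of the protocol sets objective 12, the effect of TmAg positivity on mortality, and gives its outcome measure as "Six (6) and twelve (12) month all-causes and TM-related mortality among patients who screen TmAg-positive and TmAg-negative". No symptom or disease restriction is attached.

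Section 10.3 states the sub-study hypothesis more narrowly: "asymptomatic TmAg is associated with a higher all cause morbidity and mortality". It gives the purpose as evidence for the ministry on the "potential role of screening for TmAg (and pre-emptive itraconazole therapy for TmAg-positive patients").

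The same section says "All available specimens will be tested for TmAg by ELISA in the OUCRU laboratory in Vietnam", so testing is not limited to patients free of symptoms. It also expects symptomatic positives, since it provides for their care: "The treatment regimen for those who are symptomatic will be determined by the primary physician on a case-by-case basis". For talaromycosis as a disease it cites "a mortality rate of up to 30" per cent.

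The Phase 1 exclusion criteria (section 4.2) do not name talaromycosis. The nearest criterion removes patients with over four weeks of continuous systemic antifungal treatment in the preceding six months. Under section 7.7, enrollees sent to hospital at the baseline visit for suspected meningitis or another opportunistic infection stay in the study.

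Baseline data (section 10.1.1) include "HIV-related (Date HIV testing/diagnosis, CD4 count, HIV Staging, OIs"), a symptom list and a physical examination. Section 11 plans logistic regression for factors associated with mortality and proportional hazards analysis for time to death, without mentioning TmAg.

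**The concern.** Pre-emptive treatment is aimed at people who carry the antigen but do not yet have the disease. The evidence needed is the risk in those people compared with antigen-negative patients. A pooled TmAg-positive group mixes them with patients who already have talaromycosis at enrollment and whose mortality is expected to be high on that account. If the pooled positives die more often, the plan as written cannot tell whether asymptomatic antigenemia is harmful or whether overt cases supplied the excess. The result could then be cited for screening asymptomatic patients when it says nothing about them.

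**Working it through.** **Hypothesis against comparison.** The hypothesis is about asymptomatic TmAg (section 10.3). The only stated comparison is all positives against all negatives (Table 1, objective 12). Section 10.3 separates symptomatic from asymptomatic positives for their care, but neither Table 1 nor section 11 does so for analysis.

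**Can overt disease be among the positives?** Yes.
- All available stored specimens are tested.
- Section 4.2 leaves in undiagnosed cases and those on treatment for four weeks or less.
- Section 7.7 keeps enrollees referred for another opportunistic infection.
- Section 10.3 puts the sensitivity and specificity of the assay above 90% and calls it more sensitive than blood culture, so most overt cases should test positive.

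**How large could the distortion be?** The protocol gives no sample size, power or effect size for objective 12, so there is no figure of its own to reproduce. The following is an illustration.

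Inputs:
- Overt-case mortality: 30%, the upper figure in section 10.3.
- f, the share of TmAg-positives with overt disease at enrollment: not given, assumed 10%, 25% or 50%.
- m, mortality in TmAg-negatives and also in asymptomatic positives (no asymptomatic effect): not given, assumed 5%, 10% or 15%.
- Cohort: 1,104 projected enrollees (section 6). TmAg prevalence: 5%, the minimum hypothesised in section 10.3. Positives: 0.05 × 1,104 = 55.2, about 55.

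Formulas: mortality in positives = f × 0.30 + (1 − f) × m. Spurious risk ratio = that value / m.

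Example, m = 10%, f = 25%: 0.25 × 0.30 + 0.75 × 0.10 = 0.15, and 0.15 / 0.10 = 1.50.

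| Background m | f = 10% | f = 25% | f = 50% |
|---|---|---|---|
| 5% | 7.5%, RR 1.50 | 11.25%, RR 2.25 | 17.5%, RR 3.50 |
| 10% | 12.0%, RR 1.20 | 15.0%, RR 1.50 | 20.0%, RR 2.00 |
| 15% | 16.5%, RR 1.10 | 18.75%, RR 1.25 | 22.5%, RR 1.50 |

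By construction, the comparison restricted to asymptomatic positives has a risk ratio of 1.00 in every cell.

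Chance that the pooled comparison of 55 positives with 1,049 negatives reaches two-sided p < 0.05 with no asymptomatic effect (patients treated as independent), for f = 10%, 25% and 50%:
- m = 5%: 0.17, 0.52, 0.89
- m = 10%: 0.08, 0.26, 0.62
- m = 15%: 0.05, 0.13, 0.35

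**If overt mortality is below the upper figure.** At 20% and m = 10%, f = 10% gives 0.10 × 0.20 + 0.90 × 0.10 = 0.11 (RR 1.10), and f = 50% gives 0.50 × 0.20 + 0.50 × 0.10 = 0.15 (RR 1.50).

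**What the restriction leaves.** With f = 10%, 0.90 × 55 = about 50 positives remain. With f = 50%, about 28 remain. At 10% mortality that is about 5 or about 3 expected deaths, against 5.5 in all 55.

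**The case against.** Objective 12 and its outcome measure agree with each other: both are about TmAg positivity in general, and section 10.3 also states the broader aim of assessing the clinical significance of antigenemia. That stands. A reader might infer that the outcome measure contradicts its own objective, but it does not. The conflict is with the hypothesis and intended use in section 10.3.

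Subgroups and covariates are often left to a SAP, which was not available here, and Table 1 does not forbid a split. The lack of a TmAg-specific model in section 11 is therefore no fault. But the protocol states both the hypothesis and a comparison that does not test it, and a SAP that followed Table 1 alone would carry the gap forward.

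The antifungal criterion does more than it first appears. The treatment courses described in section 10.3 run well beyond four weeks, so patients past week four of such a course in the preceding six months are excluded. Enrollees must also plan ongoing outpatient care. What remains is undiagnosed or recently started disease, and the share may be small.

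A reader might also infer that the assay was validated only on overt disease. Section 10.3 says that patients with and without culture-confirmed talaromycosis were included.

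Finally, suspected talaromycosis is not a listed baseline variable, the baseline symptoms are non-specific at this CD4 level, and a skin examination is listed only at follow-up. This bears on how the restricted group is defined, and the fix has to allow for it.

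**Conclusion.** The point holds as a mismatch between the stated hypothesis and the only stated comparison. Followed as written, the plan answers objective 12 but does not test the section 10.3 hypothesis, and overt talaromycosis at enrollment can push the pooled comparison upward.

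The size is not known. With overt-case mortality at 30%, background mortality of 10-15% and no asymptomatic effect, the spurious risk ratio is about 1.1-1.2 if 10% of positives are overt and 1.5-2.0 if 50% are. It would be larger with a lower background mortality and smaller with a lower overt-case mortality. The overt share and the background mortality are assumptions, and 30% is an upper figure that section 10.3 gives for patients presenting late.

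A reader might infer that the pooled analysis is bound to give a false signal. The documents do not support that: at a 10% overt share and 10-15% background mortality, the chance of p < 0.05 is 0.05-0.08, close to the nominal rate. The supported claim is that the pooled result, whatever its size, cannot be attributed to asymptomatic antigenemia.

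**What to change.** Add to objective 12, as the test of the section 10.3 hypothesis, a comparison of mortality between TmAg-positive and TmAg-negative participants without talaromycosis at enrollment.
- Define that group from baseline variables already recorded (opportunistic infection diagnoses, HIV stage, listed symptoms), and fix the definition before TmAg results are linked to outcomes.
- Apply the same restriction to positives and negatives, and adjust for baseline CD4.
- Report TmAg-positives with disease at baseline as a separate group.
- Keep the all-patient comparison for objective 12 as worded, and state that it is not evidence about asymptomatic antigenemia.
- Show a sensitivity analysis that restricts on recorded opportunistic infection diagnosis only, because a restriction on symptoms alone could remove many patients whose symptoms have other causes.

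The change needs no new data, visits or tests. Its cost is precision: fewer than the roughly 55 expected positives remain, with only a handful of deaths among them, so the estimate should be given with its confidence interval and a null result should not be read as absence of risk. Undiagnosed disease that the baseline record misses will still be in the restricted group, so the restriction reduces the distortion but may not remove it.

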### **3. Study design and use LFA in study and non-study sites**

This is multicenter, prospective, cohort evaluation of a CrAg screening program among HIV-infected patients with  $CD4 \leq 100$  cells/ $\mu L$  who are newly enrolled in care at selected HIV OPCs in Vietnam, conducted in collaboration with the Vietnam Administration for HIV/AIDS Control (VAAC). The evaluation will be implemented in 2 phases.

Phase 1: Enrollment in the longitudinal study will take place from August 2015-March 2017 [projected approval of the protocol amendment for Phase 2]. In Phase 1, patients with  $CD4 \leq 100$  cells/ $\mu L$  who are newly presenting for HIV care at 22 outpatient sites in the North, Middle, and South of Vietnam have been screened for cryptococcal disease by testing their plasma for CrAg using LFA and enrolled into the study for 12 months' follow-up.

Phase 2 will start in April 2017 or when the protocol amendment is approved and will continue for up to 3-6 months. After 3-6 months, transition of the program will be discussed with VAAC for continued programmatic rollout. . During this phase we will perform a cost and cost-effectiveness analysis of CrAg screening and continue CrAg screening as a routine service without enrollment in prospective follow up. CrAg tests will be made available to screen patients with  $CD4 \leq 100$  cells/ $\mu L$  including those who are treatment experienced in selected existing and additional sites, and to screen hospitalized patients with  $CD4 \leq 100$  cells/ $\mu L$  and/or suspected CNS infections in hospitals affiliated with the CRICS OPCs. CrAg testing will also be used for diagnostic purposes among patients with symptoms or signs of meningitis. We will monitor the prevalence during Phase 2 but screened patients will not be followed up prospectively in the study. As CrAg screening is a WHO and Vietnam MOH national recommendation, it is considered SOC for persons with advanced HIV ( $CD4 \leq 100$  cells/ $\mu L$ ), and reflexive testing does not require informed consent. Testing will be expanded during Phase 2 to screen other patients at selected Phase 1 and additional sites without enrolling them into follow up.

#### **Use of LFA at study and non-study facilities and laboratories in Phase 2**

CrAg screening will continue to be performed upon the completion of Phase 1. However, screened patients will not be followed prospectively.

To facilitate the implementation of CrAg screening nationally, laboratory staff and clinical providers will be made aware of the availability of LFA for screening and diagnosis. CRICS laboratories will use the LFA provided by the study to perform reflexive CrAg

screening with study LFA on specimens from patients with  $CD4 \leq 100$  cells/ $\mu L$  from OPCs included in Phase 1 and from other OPCs that are in their network, i.e., that routinely transfer specimens to these labs for CD4 count testing. LFA kits will also be used as needed for outpatient and inpatient medical wards affiliated with the participating laboratories for screening HIV patients with  $CD4 \leq 100$  cells/ $\mu L$  or with WHO stage 3 or 4 disease and for diagnostic purposes among patients with suspected meningitis.

During Phase 2, for patients who test CrAg positive, participating laboratories will inform the corresponding OPCs or inpatients wards of the results as soon as possible. The patient's primary providers will be responsible for discussing results with the patients and for prescription of fluconazole and follow up according to national guidelines. If the patient's OPC or hospital does not have fluconazole available (because of the current uncertainty of the supply of medications for opportunistic infections during the transition of financing from international donors to Vietnamese sources), fluconazole for identified CrAg positive patients will be provided by the study.

Numbers of tests and results will be documented through participating CRICS labs and tallied and will be used to in estimating the CrAg prevalence.

### **Enrollment in the follow-up study**

In Phase 1, enrollment in the longitudinal cohort will be offered to eligible patients who have  $CD4 \leq 100$  cells/ $\mu L$  enrolled at and plan to receive ongoing outpatient care at one of the selected study OPCs (Table 2). Those who test plasma CrAg-positive and have no symptoms of meningitis will be treated with high-dose fluconazole. Study participants will be followed from the time of plasma CrAg screening for a minimum of 6 months and up to 12 months depending upon when they are recruited with respect to the study expected duration. Routine clinical data will be abstracted from medical records and supplemental data will be collected to determine treatment outcomes and related factors. Fluconazole will be provided by the study for patients enrolled in the follow-up program during Phase 1 for the duration of the study. For those who tested CrAg-positive and are still receiving maintenance fluconazole at the end of their longitudinal follow up, fluconazole will be provided through routine sources.

In Phase 2, screened patients will not be followed up prospectively. However, fluconazole supply for identified CrAg-positive patients will be provided by the project if patients do not otherwise have access through their OPCs.

